Fatty acid supplementation will continue until the baby is full term (40 adjusted weeks of age). If the infant is discharged before he/she is full-term, the infant will be sent home with a bottle of the fatty acid oral solution for the infant to continue daily until he/she is full-term (40 weeks of age). The infant's nutritional needs will be carefully monitored by his/her doctor and nutritionist per NICU protocols.

To monitor the amount of fatty acid nutrition getting into the blood, we will check the infant's blood. As much as possible, we will coordinate the study blood collection at the same time as the routine NICU blood draws. We will collect 1.3 milliliters of blood at 4 different times spread apart while the infant is in the hospital. At each time point, we will collect about 1/4 teaspoon of blood, for a total of about 1 teaspoonful.

The blood draws will occur as the following four time points:

- Blood draw T0= Prior to parenteral nutrition, within 1st 3 days of life. This blood collection should be

taken from cord blood. If cord blood is not available, sample will be collected from a UAC, UVC, or peripheral blood draw concurrent with SOC.

- Blood draw T1= 5 days after parenteral nutrition is started; grace period +/-3 days therefore total 2-8 days after parenteral nutrition started.
- Blood draw T2= 5 days after enteral nutrition full feeds have arrived; grace period +/-3 days therefore total 2-8 days after full enteral nutrition arrived.
- Blood draw T3= Prior to discharge from hospital coinciding with time that ROP may be present, ≥ 35 weeks adjusted age.

This blood will be used for looking at what new genes (mRNA) the infant is making and to check how many and what kind of fatty acids the infant has in the blood. Before testing, the blood will be stored in a storage facility at the UCSD Department of Ophthalmology Blood Bank and labelled with a barcode without the infants' personal information. This is not the infant's DNA, and no DNA will be isolated or tested. Samples will be stored for 10 years. After this time point, all samples will be destroyed if not used by that time. If the parent decides to withdraw consent the blood samples that were already drawn will be destroyed, however, any previously obtained data from sample testing will be kept.

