We will examine the infant's eyes according to the standard NICU guidelines and protocols. We will also examine the infant's eyes in our eye clinic after discharge over time as we do for all premature infants to support the infant's visual development.

During the study:

Maternal diet questionnaires will be administered to the maternal subjects following enrollment. This questionnaire is the Omega 3 Fatty Acid Questionnaire and has been validated in a related study for this fatty acid¹⁹. It is anticipated to take 10-15mins to complete. Mothers will be asked to complete this questionnaire at the time of enrollment.

Blood samples will be collected 4 times. When possible, and in the majority of blood draws, 1.3 cc of whole blood will be collected at the same time as other blood draws to avoid multiple sticks. Whole blood will be collected in a green or lavender top tube. One hundred μ l of plasma will be isolated, and this will be aliquoted into in two tubes and frozen (-80°C).

Lipidomics: Plasma fatty acids will be tested using a preprandial whole-blood sample (1.3 mL) drawn 2-4 hours after the parenteral nutrition (PN) had ended for the day and after enteral feedings were held for 3 hours if the patient was also fed enterally. The schedule for sampling will be as follows: prior to parenteral nutrition within ≤ 3 days of life; within 5-8 days after parenteral nutrition is started; within 5-8 days after enteral nutrition full feeds is started; and prior to discharge from hospital coinciding with time that ROP may be present. The samples will be sent to [name] of Engineering in Medicine Laboratory at UCSD or another UCSD laboratory for internal validation of assays. [name] lab (UCSD Department of Ophthalmology) or another laboratory with similar capabilities will perform some of the RNA isolation and analysis. Capillary gas chromatography/mass spectroscopy will be the one of the main methods used to determine the phospholipid profile.

Transcriptomics: From the plasma isolated from the whole blood samples, 50 μ l will be used for mRNA isolation. This will be collected and frozen as the study is ongoing. The fold expression of genes associated with the fatty acid synthesis pathway, hypoxia and pro-angiogenic pathways will be correlated with clinical disease.

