The investigational drug pharmacy (IDS) will obtain the Omegaven and dispense it to the nurse for administration in a separate line than the rest of the nutrition (amino acids, sugars, etc). The NICU nutritionist will optimize the total nutritional calories to the infant per NICU protocols. The IDS pharmacist, nutritionist, and NICU team will not be blinded to ensure that the infant in the Omegaven group meets all the nutritional requirements as determined by the NICU neonatology attendings and fellows involved in the study. The ophthalmology team will be blinded to the treatment group to prevent any potential for bias during the eye exam.

Outcome Measures:

Outcome 1: Change in concentrations of basic fatty acids (EPA, DHA, and AA) and their bioactive metabolites will be assessed at multiple time points.

Outcome 2: Change in mRNA expression of TNF- α , PPAR- γ , and VEGF at multiple time points.

Outcome 3: Severity stage of ROP in Group 1 compared to Group 2. This will be assessed at the time of ROP screening (approximately 31 weeks), and the outcome will be measured at approximately 40 weeks adjusted age. The stage of ROP at 40 weeks adjusted will be used for statistical analyses.

Safety:

A data safety monitoring board (DSMB) will be established to monitor the safety of enrolled infants in the study as well as identifying the efficacy of the treatment at ongoing intervals. The DSMB will meet after the first 5 infants are enrolled and then regularly at multiple intervals during the study. Clinical safety assessments will occur during the hospital admission including vital signs, weight, physical exam and laboratory assessments of triglycerides. The neonatologist will review the assessments and determine if the subject should remain in the study or be removed.

Statistical Analysis

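### Outcome 2 is specified on mRNA from 50 µl of plasma, so as written it does not measure cellular gene expression, and tube type is left uncontrolled

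*Combined protocol and SAP*

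**What the plan says.** Section 9 (Research Design and Methods) of the combined protocol and SAP uses one sampling scheme for both laboratory outcomes. On volume: "We will collect 1.3 milliliters of blood at 4 different times spread apart while the infant is in the hospital". On collection: "Whole blood will be collected in a green or lavender top tube". From each draw, 100 µl of plasma is separated, divided between two tubes and frozen at −80 °C.

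Under Transcriptomics, 50 µl is taken for mRNA isolation "From the plasma isolated from the whole blood samples". Fold expression of genes in the fatty acid synthesis, hypoxia and angiogenesis pathways is then to be related to clinical disease.

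The purpose is stated after the list of blood draws: "This blood will be used for looking at what new genes (mRNA) the infant is making". Under Outcome Measures it becomes a named outcome: "Outcome 2: Change in mRNA expression of" TNF-α, PPAR-γ and VEGF at several time points. Section 6 makes gene expression pathways part of the first specific aim, beside phospholipid profiles, and the project title announces transcriptomic analyses.

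**The concern.** The specimen and the interpretation do not match. Messenger RNA that reflects what a cell is expressing sits inside the cell, and plasma is the part of the blood from which cells have been taken away. RNA found there has been released from many sources. It cannot be assigned to a cell type, or read as expression, without a justification, and the plan offers none.

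The tube rule adds a second difficulty. Outcome 2 is a change over time, so anything about collection that differs between an infant's draws enters the outcome directly. Allowing two tube types leaves one such factor open.

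At stake is the mechanistic part of the trial. Section 7 justifies the study partly by the lack of mechanistic work in the earlier Omegaven trial and the lack of clinical data on blood gene expression in severe ROP. Material is frozen while enrolment runs over 5 years, so a mismatch may surface only at analysis. A null result could then mean either no treatment effect or a specimen that does not show one.

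**Working it through.** **1. Specimen against interpretation (all in section 9).**

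| Place | What it specifies or claims |
|---|---|
| During the study | Two tube colours allowed; 100 µl of plasma kept and frozen |
| Transcriptomics | RNA comes from 50 µl of that plasma; result called fold expression |
| Purpose stated after the blood-draw list | Result shows the infant's gene activity |
| Outcome Measures, Outcome 2 | Change in mRNA expression of three genes |

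The last three interpretations all rest on the one plasma aliquot.

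**2. Is there a safeguard elsewhere?** None was found. The documents do not provide for:
- a cell fraction kept for RNA, or an RNA stabiliser;
- a time limit to plasma separation, or removal of residual cells;
- a reference gene, or an RNA yield or quality rule;
- one tube type for RNA samples.

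The storage statement speaks of blood in general, but plasma is the only frozen fraction actually specified.

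**3. Volumes.** Inputs are 1.3 mL per draw, 4 draws, 100 µl of plasma kept and 50 µl used for mRNA.
- Two equal tubes: 100 / 2 = 50 µl each, which agrees with the 50 µl for mRNA.
- Total blood: 4 × 1.3 = 5.2 mL, which agrees with the plan's statement of about one teaspoon.
- Plasma kept: 100 / 1300 = 7.7% of the draw. mRNA aliquot: 50 / 1300 = 3.8%.
- Assuming a haematocrit of 40% to 60% (not in the documents), plasma per draw is 1.3 × 0.60 = 0.78 mL down to 1.3 × 0.40 = 0.52 mL. The aliquot is then 50/780 = 6.4% to 50/520 = 9.6% of the plasma. The cell fraction, 0.52 to 0.78 mL, has no stated use.

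These figures show that the draw already contains the cells. They do not show whether 50 µl yields enough RNA, because no yield or assay limit is given.

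**4. Samples concerned.** 60 enrolled × 4 = 240 at most; 40 intended completers × 4 = 160.

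**5. What the tube rule could do.** Suppose tube type shifts measured log expression by *d*, and each draw independently uses the green tube with probability *p*. Both are assumptions, and no value for *d* is available.
- Variance added to a within-infant change = 2*p*(1 − *p*)*d*², at most *d*²/2 when *p* = 1/2.
- If the probability is *p*₀ at baseline and *p*₁ later, the mean change is shifted by (*p*₁ − *p*₀)*d*. This cancels between arms only if tube use follows the same pattern in both.

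With a single tube type, both terms are zero. Collection already varies in another way: T0 is preferably cord blood, otherwise a line or peripheral sample.

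**6. What is not touched.** The power calculation concerns DHA only (N = 40), and none is given for Outcome 2. DHA and ROP stage do not depend on the RNA specimen.

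**The case against.** The strongest reply is that cellular expression was never promised. The aims and outcomes name genes and pathways, not leukocytes; the sentence about the infant's genes is lay wording; and the disease is in the retina, so blood-cell RNA would also be a surrogate. Circulating RNA can be a legitimate analyte. This stands in part: plasma RNA may be chosen deliberately. The plan would then have to say so and interpret it accordingly, whereas it speaks of expression throughout and gives no reason for plasma.

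A second reply is that a laboratory manual may settle handling, and that the plan mentions internal validation of assays. That is possible, but no manual is among the documents, and the one specimen they define is plasma.

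A third is that, under randomisation, tube choice unrelated to allocation adds noise rather than bias to the comparison of arms. That is correct, and nothing in the documents links tube colour to arm. The noise remains, as does the possible shift in changes over time and in the planned correlation with disease.

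Finally, Outcome 2 is not the primary outcome. This is also correct and limits the weight of the point.

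**Conclusion.** The point holds in a limited form. As specified, Outcome 2 does not measure cellular gene expression, and its reading as expression is unsupported. Allowing two tube types without a rule leaves avoidable variation in it. All planned RNA samples are concerned, 240 at most. The tube point rests on the assumption that the two colours mean different anticoagulants; the documents name only colours.

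A reader might infer more, but the documents do not support it:
- *That plasma cannot show anything about expression, or contains none of the analyte.* Released RNA comes from cells and may carry an indirect signal; the documents give no yield or degradation data.
- *That heparin will inhibit the assay.* Heparin is not named, and neither an extraction method nor interference is described.
- *That the cells are irretrievably lost.* The plan states no use for them; it does not say that they are discarded.
- *That a whole specific aim fails.* Gene expression is only part of the first aim; the phospholipid part stands, as do the DHA and ROP outcomes.

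**What to change.** In section 9, under the paragraph on blood samples and under Transcriptomics:

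1. Use one tube type for all study samples: keep lavender and delete the green option.
2. Separate the plasma first and keep it for lipidomics.
3. Then add RNA stabiliser to the remaining cell pellet of the same 1.3 mL draw, freeze it, and isolate mRNA from it. The stabiliser must go on the pellet after separation: added to the whole tube at collection, it would lyse the cells and spoil the plasma.
4. State a time limit to separation, the reference gene for fold expression and an RNA quality rule.

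If plasma is kept as the RNA source, redefine Outcome 2 as circulating plasma RNA. Bring the purpose statement after the blood-draw list, the Transcriptomics paragraph and Outcome 2 into line with that, and still fix the tube type.

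The first route costs a small amount of reagent and one added handling step, with no extra blood or visit. It gives mixed blood-cell expression, which is still a surrogate for the retina and should be described as such. The second costs only wording and a tube rule, but narrows what the trial can say about mechanism. Either should be settled before further samples are collected.

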4. ESTIMATED DURATION OF THE STUDY

5 years

5. LAY LANGUAGE SUMMARY OR SYNOPSIS (no more than one paragraph)

Retinopathy of prematurity (ROP) is a blinding disease affecting infants born prematurely. These infants do not have enough essential fatty acids to structurally support the retina, the nerve tissue in the eye which allows us to see. A recent study showed that giving omega-3 (n-3) fatty acids to these infants soon after birth made them less likely to need invasive treatments for eye disease. We intend to give young infants born prematurely with n-3 fish oil treatment and look at how this changes factors in the blood that promote disease. We will do detailed blood studies comparing infants with and without ROP and will follow these infants over time to assess their eye development.

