7. BACKGROUND AND SIGNIFICANCE

Clinical:

Approximately 517,000 infants are born prematurely every year¹, and as low birth weight and premature infants are surviving longer, they are at high risk of developing severe ROP. In the United States, 2,000 infants per year are diagnosed with severe ROP, which is the leading cause of irreversible childhood blindness in the United States. In our NICU, we care for between 60 and 80 infants each year that are born with low birth weight.

Usual parenteral nutrition protocols do not meet the infants' fetal accretion rates. Despite receiving 14-28 mg DHA/kg/day,² preterm infants have lower serum DHA and EPA levels than they would have had *in utero*, and

their tissues have lower n-3 and n-6 fatty acid than full term infants, indicating that their dietary needs are often not met.³ Preterm and small for gestational age infants have altered serum phospholipid fatty acid profiles with lower DHA and polyunsaturated omega-3 fatty acids than appropriate for gestational age infants.⁴ Low birth weight infants often have severe lung disease and are exposed to exogenous oxygen, which causes retinal blood vessel attenuation, retinal hypoxia, up regulation of pro-angiogenic factors, and neovascularization, which can lead to irreversible vision loss.

In a recent Polish prospective interventional study, Pawlik et al. showed that in preterm infants (average 28 week gestation, 935 gram birth weight), continuous intravenous n-3 fatty acids with Omegaven® from day one to day 28 of life, followed by enteral omega-3 fatty acids is safe and resulted in a significantly decreased need for ROP laser treatment. In the treatment group, 9 of 60 infants needed laser compared with 22 of 70 infants in the control group.^{7,12} On treatment, infants had higher plasma and red blood cell DHA levels at 7 and 14 days and a lower risk for cholestasis. This study showed that treatment was well tolerated in preterm infants and that Omegaven® has a positive effect on ROP pathogenesis, but no investigations were done into the mechanisms by which ROP was suppressed in the experimental group compared with the control arm. There is also no clinical data that currently differentiates the differences in the blood biology (fatty acids, gene expression, and proteins) in infants with and without severe ROP.

Translational:

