9. RESEARCH DESIGN AND METHODS

The treatment duration for the study will begin 0-7 days of life and continue until 40 weeks adjusted age (full-term). Intravenous treatment will start in the first few days of life and will continue until the infant can tolerate enteral nutrition. Once enteral feeds can be started, supplementation by mouth will begin until 40 weeks adjusted age.

Laboratory blood draws:

Prior to enrollment: In addition to routine tests, blood will be tested for AST and ALT. If these tests are interpreted as abnormal, the infant will not be considered for enrollment in the study as it will be deemed a contraindication to supplemental Omegaven.

While the infant is growing in the hospital, the doctors will need to check the infant's blood to make sure the infant is developing as expected.

If the infant is enrolled in the study, the infant will be randomized in blocks of 4 by gestational age to one of two groups. The control group will get standard of care nutrition, and the experimental group will get standard of care nutrition with supplemental omega-3 fatty acids. Soon after birth, most premature infants need additional nutrition through the vein (intravenous). For the control group, there will be no changes to the standard of care parenteral nutrition. For the experimental group, the infant will receive Omegaven, an intravenous lipid preparation prepared from highly refined fish oil, in addition to the standard of care parenteral nutrition. In the instance that twins are enrolled in the study, the siblings will be randomized as one to receive the same treatment per request and approval from [name].

Transition – For the second/interventional group, Omegaven will be stopped once enteral feeds are at 120 ml/kg and enteral Oil will be started. There will be no overlap of parenteral and enteral n-3 supplementation.

If the infant can start using his/her own stomach for digestion, he/she will get fatty acid supplementation. In the control group, the infant will receive standard of care feeding. If the infant is in the experimental group, the infant will get one fourth (1/4) teaspoon per kilogram per day ($1.25\text{mL/kg/day} = 400\text{ mg omega3 per kg of fish oil per day}$) of Carlson's fish oil oral solution. Dose will be divided to at least twice a day dosing for better tolerance.

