Our primary analytic approach will use generalized linear mixed models (GLMM). These methods will address problems of missing data, variable timing of the subject visits, and other possible unintended violations of design. Although our retention and follow-up plan is designed to minimize missing data, an advantage of the GLM models is that they allow us to maximize statistical power by not excluding subjects with some missing data. More specifically, GLM assumes that the data can be missing at random (MAR) or missing completely at random (MCAR). The benefit of this assumption is with a repeated measure problem (e.g., longitudinal data) you can still analyze data from all subjects, even if some have missing data (assumed MAR or MCAR). Mixed regressions will also allow us to estimate an intercept and slope for each patient based on all available data for that individual augmented by the data from the entire sample, with two random effects being used to model time trends (i.e., a random intercept and a linear trend). Further details of selected analyses related to each outcome are provided next.

For Outcome (a-b), the primary outcome is DHA at a specified period of time (i.e. 40 weeks) to assess the basic fatty acids. Outcome (a) posits that patients in Group 1 will differ from those in Group 2 with respect to i) DHA

ii) EPA iii) AA iv) bioactive metabolites. To assess Outcome (a) (i.e. to evaluate the effects of group, time, and their interaction on the change from baseline DHA measurements), a mixed effects model with group (IV Omegaven then PO baby fish oil or Intralipid), time, and group by time interaction as fixed effects, and random intercept and slope to account for within subject correlation. We expect that the interaction in question will be significant.

For Outcome (c), we hypothesize that Group 1 and Group 2 will have a different severity stage of ROP. To assess Outcome (c), we will use a *Mixed-effects ordinal logistic regression model* with severity stage of ROP after 40 weeks (Stage I, II, III, IV, V) as the outcome variable. The same fixed and random effects mentioned above will be used in evaluating Outcome(c).

All statistical analyses will be performed using SAS software version 9.3 (SAS Institute, Cary, North Carolina, USA).

[figure not shown]
Power Calculations

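### The planned gene-expression–ROP correlation has no stated adjustment for gestational age or treatment arm, so it can be non-zero when the gene plays no part

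*Combined protocol and SAP*

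**What the plan says.** Section 9, Transcriptomics, gives the only statement of how expression will be related to eye disease: "The fold expression of genes associated with the fatty acid synthesis pathway, hypoxia and pro-angiogenic pathways will be correlated with clinical disease". The lay summary (section 5) describes a contrast by disease status: "We will do detailed blood studies comparing infants with and without ROP". Neither names a statistic, a sampling time, covariates or a way of handling the two arms.

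The Statistical Analysis text does not fill the gap. Its continuous-outcome model has group, time and "group by time interaction as fixed effects, and random intercept and slope to account for within subject correlation". The ordinal model for ROP stage takes the same effects. Expression is not a predictor in either, and neither includes gestational age.

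Gestational age appears in the design: "the infant will be randomized in blocks of 4 by gestational age to one of two groups". It is not carried into any analysis.

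Of the four blood draws, T3 is timed as "Prior to discharge from hospital coinciding with time that ROP may be present", at 35 weeks adjusted age or later.

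**The concern.** A variable that moves both expression and ROP produces a correlation between them even if neither affects the other. The protocol supplies two candidates.

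- **Immaturity.** Section 7 says premature and low-birth-weight infants are at high risk of severe ROP. It also says the oxygen that low-birth-weight infants often receive leads to retinal hypoxia, higher pro-angiogenic factors and neovascularisation. Hypoxia and pro-angiogenic genes are among those to be correlated with disease.
- **Treatment arm.** The first specific aim looks for expression differences by Omegaven treatment. The hypothesis for Outcome (c) is that ROP stage differs by arm.

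Randomisation by gestational age balances it between arms, so the between-arm mRNA comparison (Outcome 2) is protected. A correlation taken across infants compares more mature with less mature infants inside each arm, and balance between arms does nothing for that.

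Section 7 gives two gaps as motivation: the earlier trial did not study mechanism, and there are no clinical data on how blood biology differs with and without severe ROP. This analysis speaks to the second most directly. Without adjustment, a gene–ROP association could not be told apart from more immature infants having both, or from treatment having shifted both.

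**Working it through.** **Figures in the plan.** None is given for this analysis. The only power figure is for DHA: difference 42 − 27 = 15, SD 15, 20 per group, two-sided 0.05. It reproduces (86.9% by the exact t-test, against a stated value of over 80%) but does not bear on this point. From that section I take N = 40, 1:1 allocation and alpha 0.05. Applying a 0.05 test to the correlation is my yardstick; the plan states none.

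**Assumed inputs.** The documents give no correlation of gestational age (GA) with expression or with ROP severity. I take GA–ROP as -0.5 and vary GA–expression from 0.1 to 0.5. There is no direct gene–ROP link.

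**Step 1: GA only.** A common cause induces r = r(GA, expression) × r(GA, ROP). By Fisher's z, the rejection rate is approximately 1 − Φ(1.96 − atanh|r|·√(N − 3)) + Φ(−1.96 − atanh|r|·√(N − 3)), with √37 = 6.083. For a GA–expression correlation of 0.3, |r| = 0.15, atanh|r|·√37 = 0.919, and the rate is 0.149 + 0.002 = 15.1%. Simulation used 20,000 trials per setting, with continuous severity.

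| GA–expression | induced r (size) | crude, Fisher z | crude, simulated | adjusted for GA and arm |
|---|---|---|---|---|
| 0.1 | 0.05 | 6.1% | 6.2% | 5.1% |
| 0.2 | 0.10 | 9.4% | 9.3% | 4.9% |
| 0.3 | 0.15 | 15.1% | 15.1% | 4.9% |
| 0.4 | 0.20 | 23.4% | 23.9% | 5.2% |
| 0.5 | 0.25 | 34.2% | 34.5% | 4.9% |

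More infants make it worse: at N = 60 the 0.3 and 0.5 rows become 20.7% and 48.7% (Fisher z). A weaker GA–ROP link makes it milder: 0.3 for both links gives r = 0.09 and 8.5% at N = 40.

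**Step 2: arm only.** Laser rates in the cited trial were 9/60 = 15.0% and 22/70 = 31.4%. At 1:1 the arm–laser correlation is (0.314 − 0.150)/2 ÷ √(0.232 × 0.768) = 0.195. An arm effect of D SD on expression gives r(arm, expression) = D/√(D² + 4). For assumed D of 0.5, 1 and 2, the induced r is 0.05, 0.09 and 0.14, and the rejection rate 6%, 8% and 13%. Arm alone is the smaller threat.

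**Step 3: both together.** Assume treatment lowers expression by 1 SD and ROP severity by 0.5 SD. The covariance is r(GA, expression) × (−0.5) + (1 × 0.5)/4, and the divisor is √1.25 × √1.0625 = 1.152.

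| GA–expression | induced r | crude, Fisher z | crude, simulated |
|---|---|---|---|
| -0.3 (same direction as arm) | (0.150 + 0.125)/1.152 = 0.239 | 31.6% | 33.3% |
| -0.4 (same direction) | (0.200 + 0.125)/1.152 = 0.282 | 42.2% | 43.8% |
| +0.3 (opposed) | (−0.150 + 0.125)/1.152 = -0.022 | 5.2% | 4.8% |
| +0.4 (opposed) | (−0.200 + 0.125)/1.152 = -0.065 | 6.8% | 6.3% |

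The adjusted rate is 4.9 to 5.1% in all four.

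**The case against.** The strongest reply is that the plan is silent rather than wrong. The sentence on correlation sits in a laboratory-methods paragraph, the lay summary specifies no analysis, and the statistical text says it covers selected analyses. A reader might infer that the sponsor has committed to an unadjusted correlation pooling both arms. The documents do not say that; what they show is that no adjustment is specified. That part of the reply stands.

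A reader might also infer that any association will be presented as mechanism. Section 7 makes mechanism a motive for the trial, but no passage says how the result will be interpreted. The analysis is not among the three listed outcome measures and has no planned test.

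Three further limits stand.

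- The size rests on assumed correlations and is small at the low end. The higher combined figures need arm and GA to push the same way. Section 7 reports lower TNF-α with n-3 in mice and EPA depressing VEGF receptor expression, which makes that plausible for some genes, but no direction is given for infants.
- Section 7 also says "Preterm and small for gestational age infants have altered serum phospholipid fatty acid profiles". That concerns fatty acids, not mRNA, and is not evidence about gestational age within the enrolled range. The correlation sentence itself covers gene expression only, so a planned lipid–ROP correlation should not be read into it.
- Nothing says that T3 is the sample to be correlated. It would be wrong to say the plan relies on a sample taken after ROP has begun; the time point is simply unnamed.

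If expression mediates the treatment effect, an arm-driven association is not wholly spurious. A crude correlation still cannot separate mediation from two parallel effects of treatment.

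**Conclusion.** The point holds as a gap in specification with a real bias behind it. The plan proposes to correlate expression with disease and specifies no adjustment for gestational age or arm, although its own background and hypotheses link both to expression and to ROP. Gestational age is the main threat and arm the lesser one. With 40 infants, no true link and a GA–ROP correlation of -0.5, the crude false-positive rate runs from about 6 to 9% (GA–expression 0.1 to 0.2) to about 15 to 35% (0.3 to 0.5). In the combined cases tried, the arm effect moves it anywhere from about 5% to 42%. Adjustment returns it to about 5%, given that GA and arm are the only common causes, as assumed here. These rates illustrate what could happen and do not predict this trial's data. The point does not touch the primary DHA outcome or the randomised comparisons. It is worth correcting because the analysis answers a gap that motivates the study and the correction is nearly free.

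**What to change.** Replace the correlation sentence with a prespecified model, labelled exploratory:

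- Regress ROP severity on log-scale expression, with gestational age and treatment arm as covariates. Use ordinal stage, as for Outcome (c), with a category for no ROP, since the listed stages start at I.
- Allow for clustering of twins, who are randomised as one.
- Use as predictors only samples drawn before ROP is first seen: T1, and T2 when it precedes ROP. T2 is tied to full feeds and screening starts at about 31 weeks, so T2 may follow onset; report how many T2 samples qualify. T0 also precedes ROP and can serve as the pre-treatment value.
- Report T3 as a concurrent association only.
- If fatty acids are also related to ROP, use the same adjusted model.

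The cost is a paragraph of SAP text and about two degrees of freedom. Gestational age and arm are already held from randomisation, so no new data are needed. With about 40 infants few further covariates can be supported, so confounding by oxygen exposure or illness severity would remain and should be stated as a limitation.
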